#### 7.1.4. Preparation and administration procedure

TG4050 doses will be prepared and handled according to the instructions provided in a Preparation Procedure provided by Transgene.

TG4050 must be prepared under aseptic conditions in compliance with requirements for every human injectable preparation. Aseptic conditions mean the standard hospital conditions for injectable preparations that ensure the sterility of the TG4050 solutions.

Each TG4050 dose will be administered by a single SC injection. Four injection sites will be used (left and right arm, left and right thigh) according to a rotation schedule. It is preferable that the first injection is administered in either the right or left thigh. The second injection is to be given in the opposite side arm, the third in the same side thigh, and the fourth in the opposite side arm. For example, if the left thigh is the site of the first vaccination, the second vaccination would be in the right arm, the third in the right thigh, and the fourth in the left arm. This pattern is recommended and will be repeated for subsequent injections.

If the pattern cannot be followed exactly, it is more important to alternate between the arms and thighs than side to side.

In case of incident while handling TG4050, the actions recommended are described in the Technical Sheet.

Any incident must be documented by a written report to be sent as soon as knowledge of the event to Transgene Medical Department or its designee:

Emergency 24-hour telephone number (international): [name]

### 7.1.5. Disposal and destruction or return

During the course of the study based on Transgene's request and at termination of the study all unused TG4050 will be destroyed locally or returned to Transgene.

For local destruction, the Investigator/Pharmacist or delegated person will ensure that destruction is performed according to written instructions for disposal of TG4050 and waste generated during the TG4050 preparation and administration (e.g. injected and non-injected syringes, needles, gloves, etc.) available in the TG4050 Investigator's Brochure and the Technical Sheet, and will not expose humans to any risks from TG4050. A certificate of destruction will be completed and provided to Transgene (copy retained by the site).

Alternatively, unused vials of TG4050 may be returned to Transgene with the appropriate documentation. Transgene will coordinate the return of unused vials of TG4050. A certificate of return will be completed and provided to Transgene (copy retained by the site).

All along the study, the monitor will verify that all used TG4050 vials and waste linked to TG4050 handling are disposed locally, all unused/expired vials are returned or destroyed locally, and no product remains on site upon completion or termination of the study.

Accurate records of TG4050 received at, dispensed from, returned to and disposal of by the study site should be recorded appropriately on the drug log.

### 7.1.6. Supplier

TG4050 will be supplied by Transgene for this study at no cost to the study participant.

## 7.2. Treatment duration

Study treatment will be administered up to a total of 20 injections unless disease progression justifying initiation of further treatment, unacceptable toxicity including occurrence of a dose-limiting toxicity, or patient withdrawal due to any reason, whichever occurs first.

### **7.3. Treatment modification**

No dose reduction is allowed.

If a grade 1 occurs, TG4050 should be administered as planned. In case a grade  $\geq 2$  treatment-emergent AE occurs, that is at least possibly related to TG4050, the administration of TG4050 will be delayed until resolution to grade  $\leq 1$  with the following exceptions: fatigue and injection site reactions which are common vaccine-associated AEs. The decision to restart TG4050 or to permanently discontinue study treatment will be discussed between the investigator and Transgene.

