#### 4.3.2. Withdrawal from study treatment period

Patients must discontinue the study treatment (i.e., for another reason than disease progression or death) if any of the following occurs:

- Significant clinical deterioration (clinical progression), defined as new symptoms that are deemed by the investigator to be clinically significant and due to cancer growth. However, every effort should be made to document objective progression even after discontinuation of treatment
- Occurrence of a dose-limiting toxicity i.e any treatment-emergent AE grade  $\geq 3$  toxicity that is at least possibly related to TG4050, with the following exception: pre-existing grade 2 fatigue at baseline that would worsen up to grade 3
- Physician's decision that further participation in the study is not in the patient's best interest
- Patient's request at any time for any reason
- Protocol violation
- Lost to follow up
- TG4050 expiry date reached

For any discontinuation, the Investigator will obtain all the required details and document the date and the reason for the discontinuation in the eCRF. In any case of treatment discontinuation not related to disease progression the patient will be followed per protocol until documentation of disease progression.

If the reason of stopping the treatment is an AE, the specific event will be recorded in the eCRF. The Investigator will make thorough efforts to document the outcome.

As far as possible, no patient should leave the study without having undergone the end of treatment visit and the safety follow-up visit.

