###### Dose-limiting toxicity (DLT)

Any of the following treatment-emergent AE occurring during the first 6 weeks after TG4050 administration:

- any grade  $\geq 3$  toxicity that is at least possibly related to TG4050, with the following exception: pre-existing grade 2 fatigue at baseline that would worsen up to grade 3
- any death.

The occurrence of one of those events in the initial 3 treated patients will trigger study hold.

Beyond the safety run-in phase, a dose-limiting toxicity is defined as any treatment-emergent AE grade  $\geq 3$  toxicity that is at least possibly related to TG4050, with the following exception: pre-existing grade 2 fatigue at baseline that would worsen up to grade 3.

In any case, patients experiencing a dose-limiting toxicity will discontinue study treatment permanently.

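### Protocol 7.3 allows delay and possible restart after related grade 3 or higher events for which sections 4.3.2 and 8.2.2.1 require permanent discontinuation

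*Protocol*

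**What the plan says.** Below, related means judged at least possibly related to TG4050.

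Protocol 7.3 (Treatment modification) continues dosing as planned for grade 1. For a treatment-emergent event of grade 2 or higher "that is at least possibly related to TG4050, the administration of TG4050 will be delayed until resolution to grade" 1 or lower. The delay applies "with the following exceptions: fatigue and injection site reactions which are common vaccine-associated AEs". The paragraph ends: "The decision to restart TG4050 or to permanently discontinue study treatment will be discussed between the investigator and Transgene".

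Protocol 8.2.2.1 defines the DLT. In the first 6 weeks it is any related toxicity of grade 3 or higher, or any death. Later, "Beyond the safety run-in phase, a dose-limiting toxicity is defined as any treatment-emergent AE grade" 3 or higher that is related. The single exception in both periods is "pre-existing grade 2 fatigue at baseline that would worsen up to grade 3". The consequence is: "In any case, patients experiencing a dose-limiting toxicity will discontinue study treatment permanently".

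Protocol 4.3.2 lists the reasons for which study treatment must be stopped. One is "Occurrence of a dose-limiting toxicity i.e any treatment-emergent AE grade" 3 or higher, with the same single exception. Protocol 7.2, directly before 7.3, ends treatment on "unacceptable toxicity including occurrence of a dose-limiting toxicity". The synopsis and SAP 2.1.2 and 8.10.1.1 repeat the DLT rule and its consequence.

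**The concern.** Section 7.3 is where site staff would look when deciding on the next dose. Read alone, it handles a related grade 3 or 4 event by delay followed by a discussed decision, and it removes even the delay if the event is fatigue or an injection site reaction. Read alone, 4.3.2 and 8.2.2.1 leave nothing to discuss: the patient stops. One event can thus be handled in different ways depending on which section is followed.

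Safety and tolerability is the primary objective, so this touches both the protection of patients and the meaning of the tolerability summaries. A reader of the report could not tell whether a related grade 3 event followed by further injections was a protocol deviation or was managed under 7.3.

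**Working it through.** The plan gives no figure to reproduce. The check sets the two rules side by side for related treatment-emergent events, by grade and type.

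| Related event | Section 7.3 | Sections 4.3.2 and 8.2.2.1 | Compatible? |
|---|---|---|---|
| Grade 1 | Dose as planned | Not a DLT | Yes |
| Grade 2, other types | Delay to grade 1 or lower, then discuss | Not a DLT | Yes |
| Grade 2 fatigue or injection site reaction | Excepted from the delay | Not a DLT | Yes |
| Grade 3 or higher, other types | Delay to grade 1 or lower, then discuss restart or stop | DLT: permanent stop | No |
| Grade 3 or higher injection site reaction | Excepted from the delay | DLT: permanent stop | No |
| Grade 3 or higher fatigue, other than the next row | Excepted from the delay | DLT: permanent stop | No |
| Fatigue grade 2 at baseline, rising to grade 3 | Excepted from the delay | Excepted from the DLT definition | Yes |

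Three features of the text produce the incompatible rows.

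1. The trigger in 7.3 is grade 2 or higher. It is not limited to grade 2, and no clause removes DLTs.
2. The exceptions in 7.3 are wider than the one in the DLT definition. Injection site reactions appear only in 7.3, and its fatigue exception carries no condition on baseline or grade. That they apply at grade 3 is an inference from the missing limit; the protocol does not say so in words.
3. Section 7.3 makes permanent discontinuation one of two outcomes to be discussed. Section 4.3.2 makes it obligatory.

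Effect on the planned outputs:

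- **Can change with the rule followed:** adverse events leading to treatment discontinuation (SAP 8.10.1.2, Table 14.3.2.1), primary reason for stopping treatment (SAP 8.6.3.1), delayed, cancelled or stopped doses (Listing 16.2.5.3), and number of injections and relative dose intensity (SAP 7.6.2 and 8.6.1).
- **Does not change:** whether an event is a DLT. That depends on grade, relatedness and, in the first 6 weeks, death. The dosing action is not a criterion, so a patient with a qualifying event counts as having a DLT under either rule.

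Scale: SAP 4 reports 6 treated patients. One patient classified differently moves a proportion by 1/6 = 0.167, or 16.7 percentage points. This is only the weight of one patient. The documents identify no affected patient and give no rate of related events of grade 3 or higher.

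**The case against.** The strongest reply is that the documents already settle the matter. Mandatory discontinuation for a DLT is stated in the synopsis, in 4.3.2 and 8.2.2.1 and twice in the SAP, and 7.2 ends treatment on a DLT immediately before 7.3 begins. A specific, repeated and mandatory rule would normally override a general paragraph on delay. On that reading 7.3 governs only related events that are not DLTs, and its exceptions waive the delay without waiving withdrawal.

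This harmonised reading is plausible, and many sites might adopt it. But 7.3 does not state it. The phrase that opens "In any case, patients experiencing a dose-limiting toxicity will discontinue study treatment permanently" follows separate DLT definitions for the first 6 weeks and for the time beyond the run-in. Its natural sense is that the consequence holds in either period; it does not refer to 7.3. That 7.3 mentions permanent discontinuation does not remove the conflict, since it leaves the choice open.

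Other parts of the reply stand:

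- The analysis is descriptive, and the SAP lists grade, relatedness, DLT status and action taken for each adverse event. Departures in dosing would therefore be visible.
- SAP 8.10.1.1 already carries the DLT definition and its consequence. The SAP does not reproduce 7.3, so it has no internal conflict on this point.
- With the trial stopped in October 2024, the benefit for future dosing may be small.

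**Conclusion.** Section 7.3 is wrong as written and must be reconciled with 4.3.2, 7.2 and 8.2.2.1. The rules conflict for related events of grade 3 or higher, apart from fatigue of grade 2 at baseline that rises to grade 3. The possible consequences are for patient safety, discontinuations due to adverse events and injections received. Their size cannot be estimated from the documents beyond the weight of one patient in six.

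The conclusion rests on taking 7.3 literally, with no upper grade in its trigger and no grade limit on its exceptions.

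A reader might infer more than the documents support:

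- **That every related event of grade 3 or higher is affected.** The baseline fatigue case is excepted under both rules.
- **That DLT counts are distorted.** They follow from grade, relatedness and early death, not from the dosing action.
- **That the conflict falls on the commonest events.** Protocol 1.5.2 lists injection site reactions of grades 1 and 2 as common, and the rules agree at those grades. For fatigue it gives no grade.
- **That a patient was in fact dosed after a DLT.** Nothing in the documents shows this.

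**What to change.** In Protocol 7.3, state the grade range to which the delay-and-discuss rule applies, and whether its exceptions for fatigue and injection site reactions extend to events that meet the DLT definition. Add a cross-reference to 4.3.2, 7.2 and 8.2.2.1, so that each grade and event type has one consequence. Which clinical rule should prevail is for the sponsor and the investigators to decide.

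Because the study has stopped with 6 patients treated, also report for each related event of grade 3 or higher the DLT flag, the action taken with TG4050 and which rule was applied. The first two items are already in the adverse event listing planned in SAP 8.10.1.2; only the third is new. SAP 8.10.1.1 needs changing only if the reconciliation alters the DLT rule.

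The cost is one paragraph of protocol wording and one added item in the report for any such events.

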### **7.4. Treatment compliance**

#### **7.4.1. Dispensing and accountability**

TG4050 will only be dispensed, according to Investigator's prescription, to patients who meet all eligibility criteria.

The Investigator / Pharmacist or delegated person will maintain IMP accountability records for TG4050, detailing the dates and quantities dispensed for each patient along with IMP packaging batch numbers, box and vial numbers.

IMP accountability records will be verified by the monitor during site monitoring visits. All used and unused IMP will be accounted for. All unused IMP will be destroyed locally or returned to Transgene, providing destruction or return certificates (see sections 7.1.5 and 7.1.6).

#### **7.4.2. Assessment of compliance**

The compliance for the IMPs will be monitored through the IMP accountability logs and information reported on the eCRF pages.

### **7.5. Concomitant medications**

#### **7.5.1. Prohibited and/or restricted medications during study treatment**

The following medications are prohibited (unless utilized to treat a drug-related adverse event):

- Immunosuppressive agents
- Immunosuppressive doses of systemic corticosteroids (except as stated in Section 7.5.3)
- Any concurrent anti-neoplastic therapy (ie, chemotherapy, hormonal therapy, immunotherapy, radiation therapy, or another standard or investigational agents for treatment of ovarian cancer)
- Any live vaccine for the prevention of infectious disease
- Any other investigational agent

The following non-drug therapies must not be used during the study (and within 28 days before the start of trial treatment):

- Herbal remedies with immunostimulating properties (e.g., mistletoe extract) or known to potentially interfere with major organ function (e.g., hypericin)
- Major surgery

If the use of a non-permitted concomitant therapy becomes necessary during the trial, the patient should be withdrawn from trial treatment (Transgene may be contacted to discuss whether the trial treatment must be discontinued).

### 7.5.2. Permitted medications/therapies

- Patients are permitted the use of topical, ocular, intra-articular, intranasal, and inhalational corticosteroids (with minimal systemic absorption).
- The use of the following drugs will not be restricted during the course of the study: G-CSF, erythropoietin, antiemetics and analgesics.
- The use of systemic corticosteroids during the study is restricted as follows: for short term treatment ( $\leq 7$  days) of allergic reactions, or for replacement for adrenal insufficiency at doses equivalent to  $\leq 10$  mg prednisone daily.
- Any medications (other than those excluded by the study protocol) that are considered necessary for the patients' welfare and will not interfere with the trial medication may be given at investigator's discretion.

### 7.6. Medical care of patients after end of study

After a patient has completed the trial or has withdrawn early, usual treatment will be administered, if required, in accordance with the trial site's standard of care and generally accepted medical practice and depending on the patient's individual medical needs.

Upon withdrawal from study treatment, patients may receive whatever care they and their physicians agree upon.

## 8. EVALUATION

### 8.1. Evaluation of screen failure

The percentage of patients who cannot be enrolled in the treatment period and the reason that prevents patients from being treated will be evaluated.

The reasons can be:

- Failure to provide the vaccine (e.g., no mutations identified) or failure to treat (e.g., non-eligibility of the patients for the treatment period)
- Lost to follow-up

### 8.2. Evaluation during the treatment period

#### 8.2.1. Efficacy evaluation

##### CA-125 evaluation

CA-125 concentration assessed in an accredited central laboratory will be measured every 3 weeks from the start of study treatment until treatment discontinuation for any reason including documented disease progression by RECIST 1.1. For patients who stopped the study treatment before documentation of disease progression, CA-125 measurements should then be performed every 9 weeks until documented progression. A CA-125 response is defined as at least a 50 %

reduction in CA-125 concentrations from a pretreatment sample according to GCIG criteria. The response must be confirmed and maintained for at least 28 days.

CA-125 doubling time and half-life as appropriate, time to normalization will also be analyzed during the study treatment period.

### Tumor evaluation

Tumor response will be evaluated according to RECIST 1.1. Tumor assessment will be performed within 21 days prior to treatment start, at Day 43 and then every 9 weeks until disease progression justifying further treatment and will require CT-scans of the pelvis and abdomen and (X-ray or preferably CT-scan) of the chest. MRI can be used for patients who are allergic to radiographic contrast media. Throughout the study, the same assessment technique must be used.

#### 8.2.2. **Safety evaluation**

Safety assessments will consist of monitoring and reporting of all adverse events (AEs) and serious adverse events (SAEs), physical examination findings including vital signs and laboratory tests (see Appendix II).

The safety assessments will be performed according to the schedule of assessments in Appendix II-B.

##### 8.2.2.1. **Definitions**

###### Treatment-Emergent Adverse Event (TEAE)

A treatment-emergent adverse event (TEAE) is defined as a sign or symptom that emerges during treatment or within 30 days after the last dose of the study drug, having been absent pre-treatment or that has worsened relative to the pre-treatment state.

###### Adverse Event (AE)

An Adverse Event is defined as any new untoward medical occurrence or worsening of a preexisting medical condition in a clinical investigation patient administered study treatment and that does not necessarily have a causal relationship with this treatment. An AE can therefore be any unfavorable and unintended sign (such as an abnormal laboratory finding), symptom, or disease temporally associated with the use of study treatment, whether or not considered related to the study treatment.

###### Adverse reaction (AR)

All noxious and unintended responses to a medicinal product related to any dose or to a study specific procedure.

###### Dose-limiting toxicity (DLT)

Any of the following treatment-emergent AE occurring during the first 6 weeks after TG4050 administration:

- any grade  $\geq 3$  toxicity that is at least possibly related to TG4050, with the following exception: pre-existing grade 2 fatigue at baseline that would worsen up to grade 3
- any death.

The occurrence of one of those events in the initial 3 treated patients will trigger study hold.

Beyond the safety run-in phase, a dose-limiting toxicity is defined as any treatment-emergent AE grade  $\geq 3$  toxicity that is at least possibly related to TG4050, with the following exception: pre-existing grade 2 fatigue at baseline that would worsen up to grade 3.

In any case, patients experiencing a dose-limiting toxicity will discontinue study treatment permanently.

### Serious adverse events

A **Serious Adverse Event (SAE)** is any untoward medical occurrence that at any dose:

- results in death
- is life-threatening (defined as an event in which the patient was at risk of death at the time of the event; it does not refer to an event which hypothetically might have caused death if it were more severe)
- requires inpatient hospitalization or causes prolongation of existing hospitalization (see NOTE below)
- results in persistent or significant disability/incapacity
- is a congenital anomaly/birth defect
- is an important medical event (defined as a medical event(s) that may not be immediately life-threatening or result in death or hospitalization but, based upon appropriate medical and scientific judgment, may jeopardize the patient or may require intervention (e.g., medical, surgical) to prevent one of the other serious outcomes listed in the definition above.) Examples of such events include, but are not limited to, intensive treatment in an emergency room or at home for allergic bronchospasm; blood dyscrasias or convulsions that do not result in hospitalization.) Potential drug induced liver injury (DILI) is also considered an important medical event.

Suspected transmission of an infectious agent (e.g., pathogenic or nonpathogenic) via the study drug is an SAE.

Although overdose and cancer are not always serious by regulatory definition, these events must be handled as SAEs. (see Section 8.2.4).

### NOTE

The following situations do not need to be reported as SAEs:

- Elective hospitalization for pre-existing conditions that have not been exacerbated by trial treatment.
- Hospitalization which was planned before the patient consented for study participation and where admission did not take longer than anticipated.
- Hospitalization planned for protocol related treatment or protocol related procedure as per institutional standard timelines.
- Social and/or convenience admission to a hospital.
- Medical or surgical procedure (e.g., endoscopy, appendectomy); the condition that leads to the procedure is an (S)AE.
- Situations where an untoward medical occurrence did not occur (palliative care, rehabilitation, overdose without occurrence of an adverse event).
- Hospitalization for anticipated day-to-day fluctuations of pre-existing disease(s) or condition(s) present or detected at the start of the study that do not worsen.

